#### **8.4.3. Change from Baseline in HFMSE across all available assessments (Months 1-6 vs. Months 7-12) among patients $\geq 24$ months and $< 60$ months of age at time of dosing**

The weighted mean change from baseline in HFMSE total score considering all post-baseline visits from Months 1 through 6 and separately considering all post-baseline visits from Months 7 through 12 will be summarized for patients overall and by dose. All change from baseline HFMSE scores available across all post-baseline visits during the first 6 months of the trial (Months 1-6) will be averaged together for one measure, and all change from baseline HFMSE scores available across all post-baseline visits during the last 6 months of the trial (Months 7-12) will be averaged together for the second measure. The number of available post-baseline HFMSE scores available for each patient within each window (Months 1-6, Months 7-12) will be used as the weight for this calculation.

The difference between scores (Months 1-6 vs. Months 7-12) will be analyzed using an ANCOVA model which will include the weighted mean change from baseline HFMSE score as the dependent variable, time period (Months 1-6, Months 7-12), and baseline HFMSE score and age at baseline as covariates. The unadjusted means, LS means, differences between LS means, a 95% 2-sided CIs for each difference and the p-values from model effects will be reported.

This analysis will be repeated in the subset of subset of patients that achieve a  $\geq 3$ -point increase from baseline in HFMSE (Months 1-6 vs. Months 7-12) and separately in the subset of subset of patients that achieve a <3-point increase from baseline in HFMSE (Months 1-6 vs. Months 7-12), defined as follows:

- AVXS-101 treated patients with a weighted mean change from baseline in HFMSE total score of  $\geq 3$  points considering all post-baseline visits from Months 1 through 6
- AVXS-101 treated patients with a weighted mean change from baseline in HFMSE total score of <3 points considering all post-baseline visits from Months 1 through 6
- AVXS-101 treated patients with a weighted mean change from baseline in HFMSE total score of  $\geq 3$  points considering all post-baseline visits from Months 7 through 12
- AVXS-101 treated patients with a weighted mean change from baseline in HFMSE total score of <3 points considering all post-baseline visits from Months 7 through 12

The summary and statistical analysis will be conducted using the ITT Set and repeated for the ECAS, in the event the ECAS contains a subset of patients of the ITT Set.

## **9. ANALYSIS OF PHARMACOKINETICS**

Not applicable for this SAP.

## 10. ANALYSIS OF PHARMACODYNAMICS

Not applicable for this SAP.

## 11. SAFETY

The population used for safety analyses will be the SS. Safety will be assessed on the basis of AEs, clinical laboratory data, physical examinations, non-invasive ventilatory support use, vital signs and related exams. All safety analyses will be summarized overall and by actual dose received and age group. Safety data will not be compared with the PNCR natural history cohort as AE data, study product exposure, laboratory assessments, vital sign, ECG, 12-lead Holter monitor, physical examination, echocardiogram, pulmonary exam, ventilatory support and viral shedding were not collected in a comparable manner during the natural history study.

### 11.1. Extent of Exposure

The planned volume to be administered, total volume administered, duration of injection and post-injection procedure of the patients' injection of study product on the dosing date will be summarized overall and by actual dose received and age group for all patients.

Planned volume to be administered is calculated as follows: [(Cohort-specific dose for patient) ÷ (titer associated with lot number of actual administered dose)], where:

- The dose administered in Cohort 1 is  $6.0 \times 10^{13}$  vg (Dose A)
- The dose administered in Cohort 2 is  $1.2 \times 10^{14}$  vg (Dose B)
- The dose administered in Cohort 3 is  $2.4 \times 10^{14}$  vg (Dose C)

Duration of injection is calculated as (injection stop time – injection start time) and is expressed in seconds. If a patient's injection start time = injection stop time, then the duration of injection will be set as 60 seconds. If a patient's injection start time or stop time is missing, then the duration of injection will not be calculated.

A listing of injections of AVXS-101 will be provided.

### 11.2. Treatment Compliance

The treatment compliance of each patient will calculated as:

$$\text{Percentage of compliance (\%)} = 100 * (\text{total volume administered} - 1.5 \text{ mL contrast}) / (\text{planned volume administered})$$

Treatment compliance will be summarized by dose and by age group.

### 11.3. Adverse Events / Adverse Drug Reactions

#### 11.3.1. Adverse Events / Adverse Drug Reactions

Adverse events will be coded using MedDRA. TEAEs are defined as any event that begins or worsens in severity after the first injection of study product through the last study visit. If an incomplete or missing onset date was collected for an AE, the imputation method of missing data specified in Section 6.3 will be applied. The AE will be defined as TEAE if its imputed onset date is after the date and time of injection of study product through last study visit.

The Common Terminology Criteria for Adverse Event (CTCAE) version 4.03 will be applied for determining the severity of each AE. The classifications of CTCAE 4.03 are outlined in Table 6.

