 Troponin I will be measured instead of CK-MB in new patients who are screened and enrolled after amendment 5 (protocol version 6.0) goes into effect. Participants who have been screened and enrolled but who have not yet received gene replacement therapy (visit #2) at the time that amendment 5 (protocol version 6.0) goes into effect will have baseline troponin I testing prior to treatment with AVXS-101, and will have troponin I testing in place of CK-MB. CK-MB will be collected from all other participants.

 Only patients enrolled in Cohort 3 will have a month 15 visit. Patients enrolled in Cohorts 1 and 2 will complete the study or have EOS visit at Month 12

In a case where sufficient blood cannot be collected from a patient, blood will be used in the following priority order with the first having greatest priority and last having the least priority:

1. Safety blood labs: chemistry → hematology → coagulation → creatinine kinase isozyme-MB (CK-MB) or troponin
2. Interferon gamma (IFN- $\gamma$ ) ELISpot to detect T-cell responses
3. Serum antibody to AAV9 and SMN
4. Genetic re-confirmation testing

If there is not sufficient blood volume to include the genetic reconfirmation testing sample at the screening visit, the patient must return before the inpatient period. All patients must have genetic reconfirmation testing completed.

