### 2.2. Timings of Analyses

#### 2.2.1. Primary Safety and Efficacy Analysis

Patients from Cohort 1 and Cohort 2 will be followed for a total of 12 months post-dose; patients from Cohort 3 will be followed for a total of 15 months post-dose. The primary analyses for efficacy will be assessed when all patients have completed 12 months of follow-up study visits following AVXS-101 administration, and the primary analyses for safety will be assessed when the last patient of Cohort 3 reaches 15 months post-dose (and database lock will take place after the last patient reaches 15 months post-dose).

On 18-November-2021, AveXis made the decision to terminate the study early. As a result, Cohort 3 did not enroll the full number of planned patients. Per the protocol, a total of 24 patients were planned to be enrolled into Cohort 3: 12 patients aged > 6 months and < 24 months and 12 patients aged  $\geq$  24 and < 60 months. When the decision was made to terminate the study early, a total of 4 patients aged > 6 months and < 24 months had been enrolled and treated in Cohort 3. Because of the early study termination, the majority of analyses pre-specified in the protocol to be conducted on patients in Cohort 3 are no longer applicable. Unless otherwise specified, the data collected for patients in Cohort 3 will be summarized using descriptive statistics and summarized in data listings.

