### 3. STUDY OBJECTIVES

#### 3.1. Primary Objectives

##### 3.1.1. Safety

The primary safety objective is to assess the safety and tolerability of intrathecal administration of AVXS-101 by the incidence and severity of adverse events (AEs) while determining the optimal dose of AVXS-101 that demonstrates acceptable safety with maximum preliminary efficacy administered by intrathecal injection.

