Based on an ongoing assessment of safety and efficacy data from patients treated with the  $1.2 \times 10^{14}$  vg dose, an option for testing of a third dose (Dose C) will be considered. A meeting of the DSMB will be called to obtain agreement on the safety of escalating to a higher dose prior to proceeding. If, based on all available data, this is judged to be necessary, three (3) patients  $<$  60 months of age will receive  $2.4 \times 10^{14}$  vg of AVXS-101 (Dose C). If agreement is obtained from the DSMB, there will again be a four-week interval between dosing of the first three patients receiving Dose C, as in Cohorts 1 and 2. Safety data will be reviewed by the DSMB during quarterly meetings; following enrollment of the first three (3) Dose C patients and based upon available safety data, a decision will be made whether to: a) stop due to toxicity, or b) continue to enroll an additional 21 patients until there are a total of twelve (12) patients  $>$  6 months and  $<$  24 months and twelve (12) patients  $\geq$  24 and  $<$  60 months that have received Dose C.

All patients enrolled in Cohort 1 (Dose A) and Cohort 2 (Dose B) will be followed for a total of 12 months. Patients enrolled in Cohort 3 (Dose C) will be followed for a total of 15 months. The primary analyses for efficacy will be assessed when all patients in each age group reach 12 months post-dose and the primary analyses for safety will be assessed when the last patient of

Cohort 3 reaches 15 months post-dose (and database lock will be performed at the time point at which the last patient reaches 15 months post-dose). An additional analysis of efficacy and safety data was conducted when the last Cohort 2 patient completed the 12 month visit.

Safety will be assessed through monitoring AE reports and concomitant medication usage, and by conducting physical examinations, vital sign assessments, cardiovascular evaluations, laboratory evaluations, and pulmonary examinations. Patients will be observed at the hospital for 48 hours post intrathecal injection. Patients will return for follow up visits on Days 7, 14, 21, and 30. Patients will return monthly thereafter, following the Day 30 visit, according to the Schedule of Assessments. Patients in Cohort 3 who were enrolled into the study after Protocol Version 8 (Amendment 7) went into effect will return for follow up visits on Days 44 and 72 for laboratory assessments (liver function tests only).

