#### **11.3.2.1. Adverse Event Overview**

An overview of AEs will be presented by the actual treatment received overall and by dose and age group consisting of the number and percentage of patients experiencing at least one event for the following AE categories:

- Any TEAEs
- TEAEs related to study treatment
- TEAEs of Grade III (severe) severity or higher
- Serious TEAEs
- Serious TEAEs related to study treatment
- TEAEs leading to discontinuation of patient from study
- TEAEs leading to death

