For hemoglobin and the liver function enzyme (LFE) tests of ALT, AST, and alkaline phosphatase, the number and percentage of patients in each age/dose group with a maximum CTCAE Grade of 1, 2, 3, or 4 (as defined by the central laboratory and based on CTCAE v4.03) at any post-baseline visit (regardless of the baseline value) through the end of study will be summarized. All LFE tables will include summary rows for the number and percentage of patients with at least Grade 2 and at least Grade 3 laboratory abnormalities. The hemoglobin table will include a summary row for the number and percentage of patients with a Grade 3 laboratory abnormality. Accompanying listings of all ALT, AST, total serum bilirubin, direct bilirubin, and alkaline phosphatase will be created for any patients who had at least a Grade 3 ALT, AST, or alkaline phosphatase value. A listing of hematology results will be provided for patients with hemoglobin abnormalities.

The number and percentage of patients meeting the following criteria will be summarized overall and by dose and age group:

- ALT >3x ULN, ALT >5x ULN, ALT >10x ULN, ALT >20x ULN
- AST >3x ULN, AST >5x ULN, AST >10x ULN, AST >20x ULN
- ALT or AST >3x ULN, ALT or AST >5x ULN, ALT or AST >8x ULN, ALT or AST >10x ULN, ALT or AST >20x ULN
- Total bilirubin >2x ULN, Total bilirubin >3x ULN
- ALT or AST >3x ULN and Total bilirubin >2x ULN
- ALT or AST >3x ULN and Total bilirubin >2x ULN and Alkaline phosphatase  $\geq$ 2x ULN
- ALT or AST >3x ULN and Total bilirubin >2x ULN and Alkaline phosphatase <2x ULN

A patient or event will be counted if the post-baseline laboratory values meet the above criteria regardless of the baseline laboratory value (i.e., the post-baseline laboratory value does not need to be worse than the baseline laboratory value). For the last three combination categories, the values do not need to have been collected at the same assessment. For patients meeting any elevation criterion, a corresponding listing of all ALT, AST, alkaline phosphatase, and total, direct, and indirect bilirubin values will be provided.

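### By-dose adverse-event and liver tables cover 12 months for Doses A and B but 15 months, with more liver tests, for Dose C; a Month 12 cut should be added

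*SAP*

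**What the plan says.** **Follow-up.** SAP Section 2.2.1 states: "Patients from Cohort 1 and Cohort 2 will be followed for a total of 12 months post-dose"; and "patients from Cohort 3 will be followed for a total of 15 months post-dose". A footnote to Protocol Table 7 agrees: "Only patients enrolled in Cohort 3 will have a month 15 visit". Under SAP Section 3.5, Cohort 3 patients enrolled once Amendment 7 was in force "will return for follow up visits on Days 44 and 72 for laboratory assessments (liver function tests only".

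**Adverse events.** SAP Section 11.3.1 defines a treatment-emergent event as "any event that begins or worsens in severity after the first injection of study product through the last study visit". Section 11.3.2.1 tabulates the "number and percentage of patients experiencing at least one event", by dose and age group, and the AESI tables take the same form. The categories include the primary safety endpoints of Section 4.4: any, serious, related, and Grade 3 or higher events.

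**Liver values.** SAP Section 11.4.2 reports the maximum CTCAE grade "at any post-baseline visit (regardless of the baseline value) through the end of study will be summarized". The tables of ULN multiples also accept any post-baseline value.

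**Contrast with efficacy.** Protocol Section 14.6.1 makes 12 months the primary efficacy period and 15 months supportive. SAP Section 11 has no such split, no person-time rate and no common set of visits.

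**Role and size.** The primary safety objective includes "determining the optimal dose of AVXS-101 that demonstrates acceptable safety with maximum preliminary efficacy" (SAP Section 3.1.1). After early termination, Dose C has 4 treated patients, all in the younger age group, against 24 planned. They are to be summarized descriptively and listed (SAP Section 2.2.1).

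**The concern.** The proportion of patients with at least one event grows with time observed, and a worst value grows with the number of samples, even when the underlying risk is identical. Placed side by side by dose, the tables can therefore show a higher Dose C percentage that reflects only longer or denser observation.

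Liver values are the most exposed. Under Protocol Section 9.2.1 the prednisolone taper ends at Week 9, and liver tests about two weeks later are meant to look for rebound. Day 72 falls at about that time, and only Dose C has that scheduled visit. In the combined transaminase-plus-bilirubin categories of SAP Section 11.4.2, the values need not come from the same assessment, so each further visit gives another chance to complete the combination.

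At stake is how the primary safety summaries read when the doses are set next to each other.

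**Working it through.** The documents give no power, error rate or decision rule for a between-dose safety comparison, so there is no stated figure to reproduce. The check sizes the artefact on the assumption that the doses are equally toxic.

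**1. Extra follow-up time.** The inputs are 12 and 15 months (SAP Section 2.2.1), a ratio of 15/12 = 1.25. Let p be the 12-month incidence and k the hazard in Months 12–15 relative to the first-year mean. Then

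15-month incidence = 1 − (1 − p)^(1 + 0.25k).

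The documents do not give the hazard over time. Two assumed shapes are k = 1 (constant) and k = 0.25 (front-loaded).

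| p at 12 months | 15 months, k = 1 | Gain (points) | Gain × 4 patients | 15 months, k = 0.25 | Gain (points) |
|---|---|---|---|---|---|
| 10% | 12.3% | 2.3 | 0.09 | 10.6% | 0.6 |
| 30% | 36.0% | 6.0 | 0.24 | 31.5% | 1.5 |
| 50% | 58.0% | 8.0 | 0.32 | 52.1% | 2.1 |
| 70% | 77.8% | 7.8 | 0.31 | 72.2% | 2.2 |

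For k = 1 the largest possible gain is 8.2 points, near p = 59%, or 4 × 0.082 = 0.33 of a patient. For k = 0.25 it stays below 0.1 of a patient.

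**2. Extra liver tests.** Scheduled post-dose tests, from the Schedule of Assessments and Protocol Table 7:

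- Doses A and B: Days 2, 7, 14, 21, 30 and 60 (6) plus Months 3–12 (10) = 16.
- Dose C: 16 plus Days 44 and 72 and Month 15 = 19.

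If each test has an independent chance q of crossing a threshold, the chance of ever crossing is 1 − (1 − q)^n.

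| q (assumed) | n = 16 | n = 18 | n = 19 | 19 v 16, × 4 patients |
|---|---|---|---|---|
| 2% | 27.6% | 30.5% | 31.9% | 4 × 0.043 = 0.17 |
| 5% | 56.0% | 60.3% | 62.3% | 4 × 0.063 = 0.25 |

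Serial enzyme values are not independent, so these figures show only the direction and rough scale.

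**3. Sampling error.** One of 4 patients is 25 percentage points. The exact 95% interval is 0–60% for 0/4 and 6.8–93.2% for 2/4.

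**4. Effect of a Month 12 cut.** The artefact from the extra 3 months becomes zero by construction. Scheduled liver tests become 16 against 18. A display limited to visits scheduled for every dose gives 16 against 16.

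**The case against.** **These tables do not choose the dose.** A reader might infer that the by-dose tables are the sole basis for judging Dose C acceptable. The documents do not support that. Protocol Section 14.7.1.2 ties dose determination to DSMB/DMC recommendations, and the Cohort 3 review may follow the third enrolled patient (Protocol Section 15.1). SAP Section 13 says the SAP safety analysis is not planned for the DSMB. No document sets a between-dose safety test or selects a dose from the final tables. This stands. The tables remain the planned side-by-side summary of the primary safety endpoints.

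**Net bias against Dose C is not shown.** This is the other tempting inference. Amendment 7 added the liver visits, but it also tightened liver eligibility and changed the prednisolone and liver-test guidance (Protocol Appendix 3). Those changes could lower liver events in patients enrolled later. This also stands: only the direction of the observation artefact is known. Eligibility cannot be undone in analysis, whereas unequal observation can.

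**The size is small and assumption-bound.** Four patients can be read one by one in the listings. The product is given once, and the protocol points to early effects: a T-cell response at 2–4 weeks (Section 9.2.1), and transient platelet decreases managed with one month of monitoring (Section 5.5). The count of 16 against 19 covers scheduled tests only. Fifteen months is planned follow-up, and the documents do not say that all four patients reached it. All of this stands and limits the weight of the point.

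**Part is already handled.** Laboratory mean changes and vital-sign PCS counts are given by visit (SAP Sections 11.4.2 and 11.5), so they can be compared at matched visits. The cumulative AE and worst-value liver tables cannot.

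**Dropping Days 44 and 72 could hide a signal.** Amendment 7 added liver monitoring after an acute liver failure case. Removing those values from the main comparison could conceal enzyme peaks during or just after the taper. This stands and shapes the fix.

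**Conclusion.** The gap is real but minor. SAP Sections 11.3.2 and 11.4.2 put cumulative proportions side by side over 12 months for two doses and 15 months for the third, with up to three more scheduled liver tests for the third. Nothing in Section 11 equalizes the periods, although efficacy has a 12-month primary analysis.

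All else equal, the difference can only inflate Dose C; the net direction of all the differences between cohorts is unproven. For adverse events, the expected inflation among four patients is about a third of a patient at most under a constant hazard, and less than a tenth if the late hazard is a quarter of the first-year mean. Both rest on assumed hazard shapes and on all four patients reaching Month 15. Sampling error is far larger. The practical reason to act is that a single first event after Month 12, or a single crossing at an extra visit, shifts a Dose C percentage by 25 points, and the table would not show why.

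**What to change.** - In SAP Sections 11.3.2 and 11.4.2, add by-dose tables of TEAEs, AESIs, maximum CTCAE grade and ULN multiples, cut at the Month 12 visit for every dose. Make the comparison within the younger age group, where all Dose C patients are.
- Keep the full-period tables and listings beside them.
- Report follow-up time and number of liver assessments by dose. SAP Section 7.1 already allows for final visits more than 30 days late, so actual time may differ from planned.
- Keep the Day 44 and Day 72 values in the main liver tables, and flag threshold crossings seen only at those visits. A version limited to visits scheduled for every dose may be added as a sensitivity display.

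The cost is SAP wording and one added set of tables from data already collected. Dose C events after Month 12 would appear only in the full-period tables and listings, so no event is lost.

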### 13.3. Recording Adverse Events

Adverse events spontaneously reported by the patient or family and/or in response to an open question from the study personnel or revealed by observation will be recorded during the study at the investigational site. However, abnormal values that constitute an SAE or lead to discontinuation of administration of study product must be reported and recorded as an AE. Information about AEs will be collected from the time of IT injection until the end of the study. Serious adverse event information will be collected from signing of consent form until the last study visit. The AE term should be reported in standard medical terminology when possible. For each AE, the Investigator will evaluate and report the onset (date and time, if start date during inpatient period), resolution (date and time, if start date during inpatient period), intensity, causality, action taken, serious outcome (if applicable), and whether or not it caused the patient to discontinue the study.

Intensity will be assessed according to [Table 6](#) in [Section 13.1.1](#).

It is important to distinguish between serious and severe AEs. Severity is a measure of intensity whereas seriousness is defined by the criteria under [Section 13.1.2](#). An AE of severe intensity may not be considered serious.

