### **6.3. Missing Data**

Patients are allowed to withdraw from the study at any time. Analysis of quantitative and categorical variables will include data from patients with non-missing values. For continuous variables, a MMRM model may be used for the comparison between AVXS treated patients and the matching PNCR cohort.

Imputation of missing or incomplete dates will only be performed on AEs and concomitant medications for determining the timing relative to the dose of study product unless otherwise specified. The rules of imputation of missing dates are specified in Table 1 and Table 2. Partial or missing dates will be listed as recorded in the electronic case report form (eCRF). All imputed dates will be no earlier than the patients' birth date.

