**Table 1: Rules of Date Imputation: Pre-Dose Assessments**

Partial Missing Start Date	Imputed Start Date
Missing month and day, but the year is present	January 1 of that year or dose date if the year is the same as the year of dose date
Missing day, but year and month are present	First day of that month or dose date if the year and month are the same as the year and month of dose date
Missing month, but year and day are present	Missing month imputed as January

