**Table 2: Rules of Date Imputation: Post-Dose Assessments**

Partial Missing Start Date	Imputed Start Date
Missing month and day, but the year is present	Date of dose
Missing day, but year and month are present	First day of that month or dose date if the year and month are the same as the year and month of dose date
Missing month, but year and day are present	Month of dose

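### Three kinds of partly dated post-dose adverse event fail the SAP's treatment-emergent test and drop out of the TEAE tables

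*SAP*

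**What the plan says.** SAP 11.3.1 gives a general definition: "TEAEs are defined as any event that begins or worsens in severity after the first injection of study product through the last study visit". For an incomplete onset date, "the imputation method of missing data specified in Section 6.3 will be applied", and the operational test is then: "The AE will be defined as TEAE if its imputed onset date is after the date and time of injection".

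SAP 6.3 explains why dates are imputed at all. It "will only be performed on AEs and concomitant medications for determining the timing relative to the dose of study product". Two tables follow, one for pre-dose and one for post-dose assessments. Table 2 is headed "Rules of Date Imputation: Post-Dose Assessments" and has three rules:

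- Month and day missing: use the dose date. The rule does not refer to the recorded year.
- Day missing: "First day of that month or dose date if the year and month are the same as the year and month of dose date".
- Month missing: fill in the month of dosing. The recorded day is kept.

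Table 1, for pre-dose assessments, also uses the dose date in some cases. For a year-only date it says: "January 1 of that year or dose date if the year is the same as the year of dose date".

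No onset time is imputed. The only lower limit on an imputed date is the patient's date of birth. Partial dates are listed as recorded.

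On collection, Protocol 13.3 says: "Information about AEs will be collected from the time of IT injection until the end of the study". Serious events are collected from consent. An onset time is requested only for events that start during the inpatient stay. The AE summaries in SAP 11.3.2 count treatment-emergent events.

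**The concern.** The purpose of imputation here is to place an event before or after the injection. Table 2 starts from events already taken to be post-dose, yet it gives many of them a date that the next step does not accept as post-dose. A date equal to the dose date, with no time attached, is not after the date and time of injection. A date earlier in the dosing month certainly is not. The operational test thus excludes events that the general definition in the same section includes.

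Tables 1 and 2 also send some partial dates to the same place. A year-only date in the dosing year, or a day-missing date in the dosing month, becomes the dose date under both tables. The imputed date then cannot separate pre-dose from post-dose events, which is its one task.

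Safety is a primary objective, and the planned AE displays are TEAE tables. For events handled under Table 2 the error can only reduce counts. The day-missing losses all fall in the dosing month, when acute effects of a single injection would be expected to show.

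**Working it through.** The plan states no figure on this point, so there is none to reproduce. The check applies the rules as written.

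**Test.** Let D be the dose date and I the imputed onset date. Under SAP 11.3.1 an event with an imputed onset is a TEAE only if I > D.

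**Worked cases.** Dose on 20 March 2018; every true onset is after dosing.

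| True onset | Recorded | I under Table 2 | TEAE? | I under the proposed fix |
|---|---|---|---|---|
| 28 Mar 2018 | Mar 2018 | 20 Mar 2018 | No | 20 Mar 2018 |
| 5 Jun 2018 | day 5, 2018 | 5 Mar 2018 | No | 5 Apr 2018 |
| 14 Sep 2018 | 2018 | 20 Mar 2018 | No | 20 Mar 2018 |
| 10 Jan 2019 | 2019 | 20 Mar 2018 | No | 1 Jan 2019 |
| 15 Jun 2018 | Jun 2018 | 1 Jun 2018 | Yes | 1 Jun 2018 |
| 25 Jun 2018 | day 25, 2018 | 25 Mar 2018 | Yes | 25 Mar 2018 |

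The fourth case is the plainest: the recorded year alone proves that the event followed dosing. The last two show that not every partial date is lost.

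**Share lost within each missing pattern.** Assumptions: onset days spread evenly from study day 2 to the end of the period; every dose date in one calendar year taken in turn; the recorded year kept when only the month is missing. Follow-up is 360 days for Cohorts 1 and 2 and 450 days for Cohort 3. A 30-day period is added for the acute phase.

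| Missing part | 30 days | 360 days | 450 days |
|---|---|---|---|
| Month and day | 100% | 100% | 100% |
| Day only | 50.7% | 4.1% | 3.3% |
| Month only | 45.0% | 23.8% | 19.1% |

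For month-only over 360 days, 22.3% of imputed dates fall before D and 1.5% equal D: 22.3% + 1.5% = 23.8%. These are shares of events with that defect, not of all AEs.

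**Would reading *after* as *on or after* be enough?** It would bring the first two rows to 0%. Month-missing dates placed before dosing would stay lost: 44.7%, 22.3% and 17.9% over 30, 360 and 450 days. It would also leave a later recorded year overwritten by the dose date.

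**A side effect not counted above.** A month-missing date in the year after dosing is given the dosing month of that later year. It passes the I > D test, but over 360 days 30.7% of month-missing onsets receive a date beyond day 360. The TEAE period ends at the last visit, so some of these could also fail, depending on actual visit dates.

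**Weight of one patient.** Dose A: 1/3 = 33%. Dose C: 1/4 = 25% (four treated, SAP 2.2.1).

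**The case against.** The strongest reply is that the test sentence is loosely worded. Placing a post-dose event on the dose date makes most sense as a way of keeping it treatment-emergent, and a programmer may well code *on or after*. That is plausible, but the SAP does not say it. It would also not rescue month-missing dates that land before dosing.

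Second, partial dates should be rare. Onset time is requested for inpatient events, visits are frequent in the first month and monthly afterwards, serious events are reported within 24 hours of awareness, and source data are verified. This stands, and it limits the practical effect.

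Third, the events may not all be known to be post-dose. The schedule of assessments marks adverse events at screening and Day -1, and serious events are collected from consent. This also stands in part. For non-serious events, however, Protocol 13.3 starts collection at the injection, and Table 2 is by its heading reserved for post-dose assessments.

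Four stronger readings are tempting, and the documents do not support them:

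- *All partly dated events are lost.* They are not. Day-missing dates in later months and month-missing dates with a later recorded day stay TEAEs.
- *The primary safety endpoint loses them.* SAP 4.4 and 6.4.1 define the primary safety endpoints as any AE, any serious AE, any related AE and any AE of Grade 3 or higher, without reference to TEAE status. The loss falls on the TEAE tables, although these are the main planned displays.
- *Incidence is understated by 33% or 25%.* The tables count patients, so this is a ceiling for a single row.
- *A general on-or-after rule would solve it.* Table 1 also sets some partly dated pre-dose events to the dose date, so such a rule would count pre-dose serious events as treatment-emergent.

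**Conclusion.** The point holds in a limited form. As written, SAP 6.3 Table 2 and SAP 11.3.1 together misclassify three kinds of partly dated post-dose AE: year-only dates; day-missing dates in the dosing month; and month-missing dates in the dosing year whose recorded day is on or before the dosing day. This is a stated rule that gives a wrong result and conflicts with the general TEAE definition beside it. It is not merely a missing detail.

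The effect on incidence cannot be sized, because the documents do not say how many onset dates are incomplete; it is probably small. It matters most in the small dose groups and in sparse rows, such as single preferred terms, where one patient may have only one qualifying event. The events should still be visible in listings with their dates as recorded, except in the listing in SAP 11.3.2.2, which is confined to TEAEs.

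The conclusion for dates set equal to the dose date rests on reading *after* literally. The conclusion for dates set before dosing does not.

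**What to change.** For AEs handled under Table 2 only:

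1. Impute the earliest date consistent with the recorded parts and not before the dose date. If only a year is recorded and it is later than the dosing year, use 1 January of that year. If the month is missing, use the first month of the recorded year that puts the recorded day on or after the dose date. A day missing in the dosing month, or a year-only date in the dosing year, stays at the dose date.
2. Class the event as a TEAE if the imputed date is on or after the dose date, unless a recorded time shows that it began before injection.
3. State that events handled under Table 1, in practice partly dated pre-dose serious events, remain non-TEAE even when imputed to the dose date.

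A rule for a completely missing onset date should be added at the same time: SAP 11.3.1 mentions this case, but neither table covers it.

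The cost is a few lines in the SAP and a change to the date-derivation program. Listing all AEs with incomplete onset dates would show at once whether any table changes. The downside is small: a rare pre-dose event on the day of dosing, with no recorded time, could be counted as treatment-emergent.
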